3.3.5 RATIONALE FOR PATIENT-REPORTED OUTCOME ASSESSMENTS

PROs provide an understanding of the impact a treatment has on a patient. As for previous Baloxavir studies we will use patient-reported outcome measurements.

4. MATERIALS AND METHODS

4.1 PATIENTS

Approximately 30 patients with allogeneic bone marrow transplant will be enrolled in this study.

4.1.1 INCLUSION CRITERIA

Patient must meet the following criteria for study entry:

- Adult patients: Signed informed consent by any patient capable of giving consent, or, where the patient is not capable of giving consent, by his or her legal/authorized representative
- Age \geq 18 years at the time of signing the Informed Consent Form/Accent Form
- Ability to comply with the study protocol, in the investigator's judgment
- Be defined as immunocompromised*, as defined by:
 1. Have received allogeneic bone marrow transplant, or
 2. Is currently receiving treatment with chemotherapy and/or CAR-T cell therapy for hematologic malignancies (e.g., leukemia, myeloma, lymphoma), or

- 3. Received treatment with chemotherapy and/or CAR-T cell therapy for hematologic malignancies (e.g., leukemia, myeloma, lymphoma) within the past 1 year.
- Tested positive for influenza infection after the onset of symptoms using a polymerase chain reaction (PCR)-based diagnostic assay.
- Presence of (a) fever ($\geq 38.0^{\circ}\text{C}$ per tympanic or rectal thermometer; $\geq 37.5^{\circ}\text{C}$ per axillary, oral or forehead/temporal thermometer) or (b) any influenza symptoms (cough, sore throat, nasal congestion, headache, feverishness or chills, muscle or joint pain, fatigue).
- The time interval between the diagnosis of influenza and the pre-dose examinations is 48 hours or less.
- For women of childbearing potential: Agreement to remain abstinent (refrain from heterosexual intercourse):

Women must remain abstinent or use contraceptive methods with a failure rate of $< 1\%$ per year during the treatment period and for 28 days after the last dose of study treatment.

Hormonal contraceptive methods must be supplemented by a barrier method.

A woman is considered to be of childbearing potential if she is postmenarcheal, has not reached a postmenopausal state (≥ 12 continuous months of amenorrhea with no identified cause other than menopause), and has not undergone surgical sterilization (removal of ovaries and/or uterus).

Examples of contraceptive methods with a failure rate of $< 1\%$ per year include bilateral tubal ligation, male sterilization, hormonal contraceptives that inhibit ovulation, hormone-releasing intrauterine devices, and copper intrauterine devices.

The reliability of sexual abstinence should be evaluated in relation to the duration of the clinical trial and the preferred and usual lifestyle of the patient. Periodic abstinence (e.g., calendar, ovulation, symptothermal, or postovulation methods) and withdrawal are not acceptable methods of contraception.

*This study will enroll a minimum of 10 patients who have received allogeneic bone marrow transplant.

4.1.2 EXCLUSION CRITERIA

Patients who meet any of the following criteria will be excluded from study entry:

- Patients who have received more than 48 hours of antiviral treatment for the current influenza infection prior to screening
- Patients who have received Baloxavir for the current influenza infection
- Known contraindication to neuraminidase inhibitors
- Patients weighing < 40 kg

- Patients unable to swallow tablets
- Patients with known severe renal impairment (estimated glomerular filtration rate $< 30 \text{ mL/min}/1.73 \text{ m}^2$) or receiving continuous renal replacement therapy, hemodialysis, peritoneal dialysis
- Patients with any of the following laboratory abnormalities detected within 24 hours prior to or during screening (according to local laboratory reference ranges):
 - ALT or AST level > 5 times the upper limit of normal (ULN)
OR
 - ALT or AST > 3 times the ULN and total bilirubin level > 2 times the ULN
- Pregnant or breastfeeding, or positive pregnancy test in a predose examination, or intending to become pregnant during the study or within 28 days after the last dose of study treatment
- Exposure to an investigational antimicrobial within 5 half-lives or 30 days (whichever is longer) of randomization
- Any serious medical condition or abnormality in clinical laboratory tests that, in the investigator's judgment, precludes the patient's safe participation in and completion of the study
- Known hypersensitivity to baloxavir marboxil or the drug product excipients
- Known COVID-19 coinfection
- Unwilling to undergo nasopharyngeal (NP) swabs as per study schedule

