1.2 BACKGROUND ON XOFLUZA

Xofluza (also referred to as baloxavir marboxil) is a compound that exerts antiviral effects against influenza. Xofluza is a pro-drug, which is converted to an active form baloxavir through a metabolic process called hydrolysis, in the blood, liver, and small intestine.

Xofluza has a novel mechanism of action. In fact it acts on cap-dependent endonuclease, an enzyme specific to influenza viruses, and inhibits viral cap-snatching, thereby suppressing the replication of influenza viruses.

To date, one Phase II study in otherwise healthy adults and two Phase III studies in adults and adolescents (i.e., one in otherwise healthy patients and one in patients with high risk of influenza-related complications) have been completed and are summarized below. Currently, the drug is also approved for post-exposure prophylaxis, the reduction of influenza transmission, and otherwise healthy pediatrics (< 12 years of age).

Xofluza is approved for use in Japan (since February 2018) for the treatment of influenza A or B virus infection in all age groups (≥ 10 kg) and in the United States (since October 2018). It is approved for the treatment of influenza in otherwise healthy patients aged 12 years and above who have been symptomatic for no more than 48 hours. In addition, Xofluza is approved in Thailand and Japan for the treatment of influenza in patients aged 12 years and above who have been symptomatic for no more than 48 hours and are at high risk of developing influenza-related complications. Currently baloxavir is approved for influenza treatment in more than 60 countries).

Detailed profiles of Xofluza are provided in the Xofluza Investigator's Brochure.

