1.3 STUDY RATIONAL AND BENEFIT-RISK ASSESSMENT

Seasonal influenza is a major burden to global health. There are an estimated 3–5 million cases of severe disease worldwide and approximately 290–650 thousand people die from influenza annually (WHO 2017a, WHO 2018, Baxter 2016). Influenza also places significant demands on healthcare services each season, and impacts society through lost workforce productivity (WHO 2018). Influenza virus infection can be especially severe in stem cell transplant (SCT) recipients. In these patients the clinical course is often prolonged with a higher frequency of progression of the disease to the lower respiratory tract, protracted viral shedding and increased death^{1,2}. Neuraminidase inhibitors (NAI), including oseltamivir, are the mainstay of influenza therapy. However, because the paucity of initial symptoms and the frequent absence of fever^{3,4} the diagnosis of influenza is often delayed in this population, and treatment with NAI is often started later than 48-hours after the onset of influenza, that is the period during which NAI

treatment is most effective. Moreover, while low rates of NAI resistance are reported in the general population, high viral replication associated with prolonged therapeutic courses favor the rapid emergence and transmission of NAI-resistant influenza in SCT recipients⁵.

Baloxavir (XofluzaTM) is a first-in-class influenza antiviral that blocks influenza virus RNA replication by inhibiting cap-dependent endonuclease activity (Omoto *et al* 2018). Baloxavir has a prolonged half-life allowing the administration in single dosing and it was recently approved for use in the US for the treatment of uncomplicated influenza. In the Phase III CAPSTONE-1 double-blind randomized study in otherwise healthy patients (Hayden *et al* 2018), a single treatment of baloxavir (40 mg for patients <80 kg and 80 mg for patients ≥80 kg) significantly reduced the time to alleviation of symptoms compared with placebo and also effectively reduced viral load, as shown by a significant reduction compared with placebo in:

- The proportion of patients with positive influenza titer between Days 2 and 5
- The proportion with positive influenza virus RNA determined by PCR on Day 5
- The median time to cessation of viral shedding

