4.4.3 PROHIBITED THERAPY

Use of the following concomitant therapies is prohibited as described below:

- Investigational antimicrobial therapy (other than the protocol-mandated study treatment) is prohibited within 5 half-lives or 30 days (whichever is longer) prior to initiation of study treatment and during the study
- Concomitant use of herbal therapies is prohibited as their pharmacokinetics, safety profiles, and potential drug-drug interactions are generally unknown

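### The prior-baloxavir exclusion turns on why the drug was given, not on exposure, so a patient with recent prophylactic baloxavir can be randomised, including to placebo

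*Combined protocol and SAP*

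**What the plan says.** Two exclusions in section 4.1.2 deal with earlier anti-influenza drugs, and both refer to the present illness: "Patients who have received more than 48 hours of antiviral treatment for the current influenza infection prior to screening" and "Patients who have received Baloxavir for the current influenza infection". Neither gives a look-back period for drug taken for another reason.

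The one washout rule in the same list is "Exposure to an investigational antimicrobial within 5 half-lives or 30 days (whichever is longer) of randomization". Section 4.4.3 repeats it for concomitant therapy: "Investigational antimicrobial therapy (other than the protocol-mandated study treatment) is prohibited within 5 half-lives or 30 days".

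On the drug itself, section 1.2 states: "Currently, the drug is also approved for post-exposure prophylaxis, the reduction of influenza transmission, and otherwise healthy pediatrics". It adds: "Currently baloxavir is approved for influenza treatment in more than 60 countries". Section 1.3 states: "Baloxavir has a prolonged half-life allowing the administration in single dosing". No numeric half-life appears anywhere.

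Section 4.3 names baloxavir in combination with oseltamivir as the investigational product. It stratifies randomisation by hospitalisation and influenza type A only. Sections 4.4 and 4.5.2 collect prior medication from 7 days before study treatment. The Statistical Considerations section analyses patients who have both a baseline and a Day 10 viral load, and has no rule or covariate for earlier baloxavir.

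**The concern.** The plan tolerates up to 48 hours of other antivirals for the current infection but no baloxavir at all. It therefore already treats prior test drug as incompatible with the comparison. Yet whether a dose excludes a patient depends on its indication: a dose taken after diagnosis excludes, while the same dose taken shortly before symptoms as prophylaxis does not. How long the drug persists does not depend on why it was given.

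A placebo patient with residual baloxavir has received part of the experimental treatment, which pulls the arms together on the second co-primary endpoint, the between-arm difference in change of viral load. Separately, virus that emerged under baloxavir may already carry a PA variant of the kind section 1.3 associates with resistance. Such a variant would be a baseline finding rather than a treatment-emergent one.

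**Working it through.** **Does any other rule catch this patient?** Take a patient given marketed baloxavir as prophylaxis some days before confirmed influenza.

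- *Baloxavir exclusion (4.1.2):* the dose was not given for the current infection, so on a plain reading it does not exclude. An investigator could argue that prophylaxis for this exposure counts; the text does not say so.
- *48-hour antiviral exclusion (4.1.2):* limited to the current infection in the same way.
- *Investigational-antimicrobial washout (4.1.2, 4.4.3):* marketed baloxavir in routine care is not investigational in the ordinary sense. Against that, 4.3 calls it part of the investigational product, and 4.4.3 carves study treatment out of the ban, which may imply that it belongs to the class. The rule is ambiguous for this case.
- *Stratification, analysis set, covariates:* none uses prior baloxavir.
- *Medication history (4.4, 4.5.2):* a dose more than 7 days before study treatment need not be recorded, so analysis could not reliably repair the problem.
- *Pre-treatment sequencing (3.1, 4.2.1):* can identify a PA variant at baseline but cannot remove residual drug.

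**Reproducing the plan's figure.** Inputs from Statistical Considerations: 15 per arm, two-sided 0.05, 80% power, effect 1.1 SD. For a two-sample t-test with 28 degrees of freedom, the noncentrality is δ × √(15 × 15 / 30) = 2.739δ. The effect detectable with 80% power is 1.06 SD, which rounds to the stated 1.1. At exactly 1.1 SD the noncentrality is 3.01 and power is 82.8%. The plan's figure is not in dispute.

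**Illustrating dilution.** Let k of the 15 placebo patients carry a share f of the baloxavir effect from an earlier dose. The expected contrast becomes δ′ = 1.1 × (1 − k·f/15). Neither k nor f is in the documents. I assume k from 0 to 2 and show f at 1 (complete) and 0.5. The last column also lets the control-arm variance grow because that arm is then a mixture: it adds (k/15)(1 − k/15)(1.1f)² to a variance of 1, averages this with the other arm's variance of 1, and divides δ′ by the square root of the result.

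| k | f | δ′ (SD) | Power | Power with mixture variance |
|---|---|---|---|---|
| 0 | – | 1.100 | 82.8% | 82.8% |
| 1 | 1 | 1.1 × 14/15 = 1.027 | 77.5% | 75.9% |
| 2 | 1 | 1.1 × 13/15 = 0.953 | 71.2% | 68.3% |
| 1 | 0.5 | 1.1 × 14.5/15 = 1.063 | 80.3% | 79.9% |
| 2 | 0.5 | 1.1 × 14/15 = 1.027 | 77.5% | 76.8% |

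Here k counts placebo patients only. Under 1:1 allocation, two affected patients among the 30 enrolled give on average one on placebo. The table leaves out any lowering of the Day 1 load by residual drug. That would reduce the room to fall in either arm, and randomisation balances it on average.

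**The case against.** The strongest reply is that nothing shows the situation arises. Section 1.2 says baloxavir is approved for prophylaxis; it does not say that this clinic or population uses it that way. If no such patient enrols, there is no effect. The sample size is set by feasibility, the plan says it is probably under-powered, and it calls all between-arm comparisons exploratory. A few points of power on an assumed count matter little in that setting. All of this stands, and it keeps the point minor.

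Four stronger readings that a reader might infer are not supported:

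- *Such a placebo patient is in effect a combination patient.* The combination arm is dosed on Days 1, 4 and 7, and section 1.2.1 links repeat dosing in hospitalised patients to sustained concentrations. An earlier prophylactic dose that failed to prevent infection is not shown to be equivalent. Complete carry-over is an upper limit on f.
- *Every affected patient costs 1/15 of the contrast, whichever arm is drawn.* Residual drug dilutes only through placebo patients and needs virus that still responds. The resistance argument needs virus that no longer responds, and reduces the effect in the combination arm. The two mechanisms do not apply to the same patient.
- *Any baloxavir earlier in the season matters.* With no half-life in the documents, residual drug from a remote episode is unsupported. Treatment of an earlier episode is relevant only if it falls within whatever window is adopted.
- *The 48-hour criterion also needs to count neuraminidase-inhibitor prophylaxis.* Both arms receive oseltamivir, so such prophylaxis does not put the test drug into the control arm.

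The ambiguity over the washout also cuts both ways. Some investigators might apply it to marketed baloxavir, others would not, and that is itself a reason to settle the wording.

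**Conclusion.** The gap is real on the plain text: recent prophylactic baloxavir does not clearly exclude a patient, and nothing in the randomisation or analysis deals with it. Randomisation balances prior exposure on average, so the expected harm is a diluted contrast and some chance imbalance at 15 per arm, not bias toward baloxavir. Baseline PA variants are a possible second consequence, one that the planned sequencing can identify.

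The size is unknown. For one or two affected placebo patients, the loss from 82.8% power is about 5 to 12 percentage points at complete carry-over (82.8 − 77.5 = 5.3; 82.8 − 71.2 = 11.6). At half carry-over it is about 3 to 5 points (82.8 − 80.3 = 2.5; 82.8 − 77.5 = 5.3). The mixture variance adds at most 2.9 points (71.2 − 68.3). These figures assume a true effect of 1.1 SD and an assumed count and carry-over share. Minor, but cheap to close.

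**What to change.** Reword the exclusion in 4.1.2 to cover baloxavir received for any reason, treatment or prophylaxis, within a stated window before randomisation. The longer of five half-lives and 30 days, already used in that list for investigational antimicrobials, is one available choice. The sponsor should confirm the window and express it in days, since the protocol gives no half-life. This also removes the need to decide whether the investigational-antimicrobial rule reaches marketed baloxavir.

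Extend the 7-day medication history in 4.4 and 4.5.2, for baloxavir only, to the same window; otherwise the criterion cannot be verified. Leave the 48-hour criterion as it is on this point.

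The cost is one line of eligibility wording, a slightly longer history question at screening, and the loss of the few candidates, if any, with recent baloxavir exposure.

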4.2 SAMPLE COLLECTION AND PROCESSING

4.2.1 NASOPHARYNGEAL SAMPLING AND VIROLOGICAL ASSAYS

Two nasopharyngeal swabs will be collected at each visit and put immediately into viral transport medium and frozen. Pharyngeal swabs will be collected when if it is not possible to collect nasopharyngeal swabs. At the end of the clinical study period, samples will be used for viral sequencing and virological assessment.

Viral RNA in pre- and last post-treatment swab samples will be extracted using conventional RNA extraction kit without virus amplification and used for viral RNA quantification by q-PCR and for viral sequencing. Swabs will also be used to calculate viral titers by plaque assays on MDCK cells.

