2. OBJECTIVES AND ENDPOINTS

2.1 PRIMARY OBJECTIVE

The primary objective is to evaluate the efficacy of both the combination therapy of baloxavir with oseltamivir and that of oseltamivir plus placebo in SCT patients with influenza as measured by changes in influenza viral RNA loads at day 10 from baseline (day 1) and compare between arm differences in decline of viral load

The co-primary efficacy endpoints are:

- Change of influenza viral RNA loads from baseline (day 1) at the end of treatment (day 10) as measured by quantitative real time polymerase chain reaction (qRT-PCR, nucleic acid).
- Between-treatment-arm difference in the change of influenza viral RNA loads from baseline (day 1) at the end of treatment (day 10) as assessed by quantitative real time polymerase chain reaction as measured by (qRT-PCR, nucleic acid) and by Influenza plaque assay (replicating virus).

The secondary efficacy endpoints are:

1. **Change of influenza viral RNA load from baseline (day 1) at day 4 and day 7 and 10** as measured by quantitative real time polymerase chain reaction (qRT-PCR, nucleic acid) in each treatment arm.
2. **Difference in change of influenza viral loads from baseline (day 1) at day 4, 7 and 10 between the two treatment arms** as measured by quantitative real time polymerase chain reaction (qRT-PCR, nucleic acid)
3. **Change of influenza viral loads from baseline (day 1) at day 4, 7 and 10** as measured by Influenza plaque assay (replicating virus) in each treatment arm.
4. **Difference in change of influenza viral loads from baseline (day 1) at day 4, 7 and 10 between the two treatment arms** as measured by Influenza plaque assay (replicating virus).
5. **Time to Improvement of Individual Influenza Symptoms** [Time Frame: From Day 1 pre-treatment up to Day 30] defined as the time from the initiation of the study treatment to the improvement of influenza symptoms as assessed by patient-reported outcome measures on a single scale as specified in section 4.5.7. Time to improvement of symptoms is defined as the time from the start of treatment to the time when each of the influenza symptoms will be alleviated, maintained, or improved, for a duration of at least 24 hours.

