Participants will assess the severity of 7 influenza-associated symptoms (cough, sore throat, headache, nasal congestion, feverishness/chills, muscle/joint pain, and fatigue) on a 4-point scale (0 = no symptoms, 1= mild, 2 = moderate, and 3 = severe) as specified in section 4.5.7. Improvement is defined as: improvement pre-existing symptoms (i.e cough, fatigue, or muscle/join pain that existed prior to influenza) that were worse at baseline and improve at least 1 point from baseline; pre-existing symptoms not worse at baseline that maintain baseline severity; and new symptoms that are alleviated, defined as a symptom score of non (0) or mild (1).

Once all patient's influenza symptoms are alleviated, maintained, or improved (hereafter all will be called 'improvement') as defined above, the endpoint will be reached.

6. **Percentage of patients who experience each influenza-related complication** (hospitalization, death, sinusitis, otitis media, bronchitis, and radiologically-confirmed pneumonia) as an adverse event after the initiation of study treatment symptoms [symptoms [Time Frame: From Day 1 pre-treatment up to Day 30].
7. **Time to Return to Preinfluenza Health Status** [Time Frame: From Day 1 pre-treatment up to Day 30]. Participants will be asked to record their preinfluenza health status on a scale from 0 (worst possible health) to 10 (normal health [for someone same age and condition]), and their health status at baseline and every day after initiation of study treatment on the same scale as specified in section 4.5.7. Return to preinfluenza health status is defined as time from the initiation of the study treatment to the first time when the health status score was equal to or higher than the preinfluenza health status score.
8. **Time to viral clearance**, as assessed by difference in Percentage of Participants Positive by Influenza plaque assay and qPCR at each time-point (in each treatment group) The definition of the time to sustained cessation of infectious virus detection is the time

between the start of treatment and when virus titer remained below the detection limit on all subsequent sampling time points.

9. Measure treatment-emergent variants of neuraminidase and polymerase known to confer antiviral resistance to oseltamivir in each arm by direct next-generation sequencing symptoms [Time Frame: From Day 1 pre-treatment up to Day 30]

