3. STUDY DESIGN

3.1 DESCRIPTION OF THE STUDY

This is a randomized double-blind placebo-controlled pilot study of the efficacy and safety of baloxavir in combination with oseltamivir (SOC) for the treatment of influenza in allogeneic stem cell transplant patients.

30 SCT recipients with influenza will take part in the study. Participants will be randomly assigned (1:1) to either baloxavir + oseltamivir or baloxavir-matched placebo +oseltamivir. Randomization will be performed by research pharmacy using an interactive web randomizer. Before randomization, patients will be stratified by hospitalization status (yes or no), influenza type A (yes or no).

Patients in the baloxavir combination arm will receive weight-adjusted baloxavir (40 mg for patients weighing <80 kg and 80 mg for those weighing \geq 80 kg) at baseline and at day 4 and day 7. They will also receive oseltamivir 75 mg twice daily for 10 days.

Patients in the baloxavir-matched placebo + oseltamivir arm will receive baloxavir-matched placebo at baseline and at day 4 and day 7 and oseltamivir 75 mg twice daily for 10 days.

Nasopharyngeal swabs will be collected on days 1 (at diagnosis, pre-meds), 2, (optional visit), 4, 7 and 10 for viral quantitation and viral sequencing. Influenza virus polymerase and neuraminidase sequencing will be also performed in all patients. Patients will have follow-up visits day 15 (+/- 2 days) and day 30 (+/- 2 days, EOT). Patients who will not clear the virus by day 10 will perform additional NP swabs at these visits.

Paracetamol (acetaminophen; maximum 3000 mg per day) or NSAIDS can be given for severe discomfort or fever. No other antiviral drugs for the treatment of influenza, will be permitted, except antibiotics for the treatment of suspected bacterial infections.

For the first 10 days, patients will receive a daily call from one member of the study team to review symptoms and severity scale.

To assess the **time to improvement of individual influenza symptoms** (with modification for preexisting symptoms), participants will be given a diary to self-assess the severity of seven influenza-associated symptoms on a four-point scale. To evaluate patient-reported **time to return to pre-illness health status**, patients will also rate **daily the interference of influenza symptoms in daily activities** on a 5-point severity scale.

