For the first co-primary objective, the effects of the study drugs will be evaluated separately for each study arm by estimating the change in viral RNA loads from baseline (day1) at the end of treatment (day10) as measured by qRT-PCR. Summary statistics including mean, standard deviation, median and range of the primary endpoints will be calculated for each arm. Difference in log transformed viral RNA loads measured at the end of treatment and at baseline will be evaluated using paired t-test or the Wilcoxon signed rank test for each arm separately. For the second co-primary endpoint, efficacy of the baloxavir + oseltamivir will be assessed through estimating the differences in the magnitude of change in viral RNA loads from baseline at the end of treatment between the two treatment arms along with the 95% confidence intervals. Given the pilot nature of the study, the sample size is primarily based on feasibility and logistic considerations. However, based on prior studies [ref: Infect Dis Ther (2019) 8:613–626], the expected baseline viral RNA loads for the immunocompromised patients would be around $6.5 \log_{10} \text{vp/mL}$ with standard deviation around $3 \log_{10} \text{vp/mL}$. With 15 patients in a study arm, we would have 80% power to detect a difference of $2.33 \log_{10} \text{vp/mL}$ in viral RNA loads at the end of treatment vs. at the baseline assuming similar level of standard deviation at the end of treatment with a two-sided 0.05 significance level using a paired t-test. We expect to have adequate power to detect this level of change for both the study arms since prior study has observed a decrease of at least $3 \log_{10} \text{vp/mL}$ with Oseltamivir alone in immune compromised patients [ref: Infect Dis Ther (2019) 8:613–626]. For the second co-primary endpoint, i.e., the between arm differences in change in viral loads, 15 patients per arm will allow 80% power to detect effects size as small as 1.1 standard deviation at a two-sided 0.05 significance level. It is likely the study is under-powered but is expected to generate meaningful preliminary efficacy data [Machin, D, Campbell, M.J., Tan, S.B, Tan, S.H. 2018. 'Sample Sizes for Clinical, Laboratory and Epidemiology Studies, Fourth Edition', Chapter 16. John Wiley and Sons. Hoboken, New Jersey.].

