For secondary viral loads related endpoints, summary statistics in terms of mean, standard deviation, median and range will be calculated for each arm at each time points among patients with relevant measurements. Longitudinal analyses using mixed effects repeated measures will be used to model the mean viral loads overall time. Contrasts of interest including between arm differences will be explored using simultaneous tests of general linear hypotheses. If normality is a concern, log-transformed and standardized viral load data will be used. Longitudinal analysis will be carried out among patients with at least one relevant viral load measurement. Kaplan-Meier estimates will be generated for time to events endpoints such as time to Improvement of Individual Influenza Symptoms, the time to viral clearance and time to return to preinfluenza health status for each study arm. Between study arm difference in these endpoints will be explored using the generalized Wilcoxon test.

Categorical data such as the occurrence of treatment-emergent variants of neuraminidase and polymerase by direct next-generation sequencing and AE's will be summarized in terms of counts and proportions separately for each arm.

Between arm difference in the categorical variable will be explored using Fisher's exact test. The study is likely will not have adequate power to detect between arm differences and all the between arms comparisons are considered exploratory. Summary statistics generated for study endpoints for each arm will provide useful information for planning future studies.

The power calculations were performed using PASS 15 Power Analysis and Sample Size Software (2017). NCSS, LLC. Kaysville, Utah, USA, ncss.com/software/pass. All comparisons will be two-tailed, with a significance level at 0.05 and 95% confidence intervals will also be reported. All analyses will be performed in SAS Version 9.4 (2019), SAS Institute, Inc., Cary, NC; and R Version 4.0.4 (2021).

Note: The statistical considerations section was written by [name], MS, and revised by [name], in the Division of Biostatistics, Department of Population Health Sciences, Weill Cornell Medicine.

Influenza sequence analysis will be performed by [name], Director of Systems Genomics Section at the Laboratory of Parasitic Diseases of NIAID/NIH and expert in Influenza evolution.

No interim analysis is planned for this study

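### Section 4.2.1 names only two swabs per patient for viral RNA assay, but the secondary RNA endpoints and the repeated-measures model need days 4 and 7 as well

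*Combined protocol and SAP*

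**What the plan says.** **RNA assay.** Section 4.2.1 states: "Viral RNA in pre- and last post-treatment swab samples will be extracted using conventional RNA extraction kit". The same sentence assigns that RNA to qPCR quantification and to sequencing. The next sentence, on plaque assays, has no limit on time points.

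**What other sections need.**
- Section 3.1 collects swabs on days 1, 2 (optional), "4, 7 and 10 for viral quantitation and viral sequencing".
- Section 2.1, secondary endpoint 1: "Change of influenza viral RNA load from baseline (day 1) at day 4 and day 7 and 10". Endpoint 2: "Difference in change of influenza viral loads from baseline (day 1) at day 4, 7 and 10 between the two treatment arms", by qRT-PCR.
- Endpoint 8 uses "Percentage of Participants Positive by Influenza plaque assay and qPCR at each time-point".
- Statistical Considerations says that secondary viral load summaries "will be calculated for each arm at each time points among patients with relevant measurements", and adds: "Longitudinal analyses using mixed effects repeated measures will be used to model the mean viral loads overall time".
- The first co-primary analysis uses the "change in viral RNA loads from baseline (day1) at the end of treatment (day10) as measured by qRT-PCR".

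**Day 15 and day 30 swabs.** Section 3.1 asks for them from patients who have not cleared virus by day 10. Section 4.2.1 takes two swabs at every visit, and the Appendix 1 flowchart marks a swab at both days. Section 4.2.1 also freezes the samples and leaves virological work to the end of the clinical period.

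**Resistance.** Endpoint 9 covers neuraminidase and polymerase variants that confer resistance to oseltamivir. Section 1.3 reports that the PA I38X polymerase variant emerges under baloxavir and is associated with resistance to that drug.

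**The concern.** The sentence in Section 4.2.1 is the one the laboratory will work from. If it is followed, there is no RNA value at day 4 or day 7. Endpoints 1 and 2 then cannot be computed at those days, the qPCR part of endpoint 8 has gaps, and the longitudinal RNA model reduces to a before-and-after comparison.

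The limit also applies to sequencing. Where day 10 RNA is undetectable, the single named post-baseline swab cannot be sequenced, so a variant present on day 4 or 7 would be missed. Section 1.3 gives lower incidence of drug-resistant variants as an aim of the study.

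The last post-treatment swab is not defined. Oseltamivir runs through day 10 and some or all patients have later swabs, so the term could be taken to mean day 15 or day 30.

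**Working it through.** **1. The plan's power figures.** They do not depend on this point; they are checked only to show that nothing in them moves.
- Within arm: n = 15, difference 2.33, SD of the change taken as 3, two-sided 0.05. The noncentrality is (2.33/3) × √15 = 3.01 on 14 df, which gives power of 79.9%. The stated 80% reproduces.
- Between arms: 15 per arm, 1.1 SD. The noncentrality is 1.1 × √(15/2) = 3.01 on 28 df, which gives power of 82.8%. The effect with exactly 80% power is 1.06 SD, which rounds to the stated 1.1.

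The RNA part of both co-primary comparisons uses days 1 and 10 only.

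**2. RNA coverage.** Inputs: 30 patients (Statistical Considerations), swab days from Section 3.1, two swabs per patient from Section 4.2.1, no dropout, last swab taken as day 10.

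| Count | Scheduled | Named in 4.2.1 | Left out |
|---|---|---|---|
| Days 1, 4, 7, 10 | 30 × 4 = 120 | 30 × 2 = 60 | 60 (60/120 = 50%) |
| Adding optional day 2 for everyone | 30 × 5 = 150 | 60 | 90 (90/150 = 60%) |
| Change values for endpoints 1 and 2 (days 4, 7, 10) | 30 × 3 = 90 | 30 × 1 = 30 | 60 (60/90 = 67%) |

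Time points in the RNA model fall from 4 (5 with day 2) to 2.

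**3. Could the limit be meant for sequencing alone?** No. The sentence names qPCR as well, and Section 3.1 assigns sequencing to the same swab days as quantitation. Endpoints 3 and 4 rest on the plaque assay and are unaffected.

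**4. Day 15/30 swabs.** Taken from everyone: 30 × 2 = 60 patient-visits. Under Section 3.1: between 0 and 60, depending on clearance. That rule needs a day 10 result while the patient is still in follow-up. No test is specified for it: study assays are run after the clinical period, and the only RT-PCR timing given in Appendix 1 (footnote l) is screening. Footnote f nevertheless assumes that shedding after day 10 is known. Endpoint 8 requires virus to stay below the detection limit at all later samples; under Section 3.1, a patient first negative at day 10 has none.

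**5. Endpoint 9.** Read literally, its oseltamivir limit leaves out PA I38X. The aim in Section 1.3, the polymerase sequencing of all patients in Section 3.1 and the categorical analysis in Statistical Considerations carry no such limit.

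**The case against.** The strongest reply is that the intention is clear from the rest of the protocol. Section 4.2.1 does not say that other swabs are excluded. The sentence before the RNA sentence speaks of samples in general, footnote l of Appendix 1 introduces the swab row as being for RT-PCR, and Sections 2.1 and 3.1 and the analysis text all point to assays at every time point. On this view the percentages describe one literal reading and not an expected loss. The 60% figure further assumes that all patients attend an optional visit. The swabs are frozen, so nothing is irrecoverable, and this is a pilot whose between-arm comparisons are declared exploratory.

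Much of this stands as a limit on the consequences. It does not remove the conflict: the general sentence and the footnote do not override the one sentence that says which samples are extracted and for which assays.

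On the side issues, the flowchart's superscripts look unreliable. The day 15/30 conflict therefore rests mainly on Section 3.1 against Section 4.2.1, and it is a request for clarification. Endpoint 8 can still be computed as defined. For endpoint 9, the analysis text already summarises neuraminidase and polymerase variants by arm without an oseltamivir limit, so the defect lies in the endpoint's wording. How often the missed-variant case would occur cannot be estimated from the documents.

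**Conclusion.** The concern holds and should be fixed. As written, Section 4.2.1 contradicts Sections 2.1 and 3.1 and the longitudinal analysis. The coverage loss calculated above assumes that the laboratory follows the sentence literally, that all 30 patients complete every scheduled visit, and that the last swab is day 10.

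There is no effect on sample size, alpha or co-primary power. Section 2.1, Section 3.1 and Statistical Considerations already point to day 10 as the end-of-treatment sample, so defining the term is a clarification. The endpoint 9 wording is also wrong against the protocol's own rationale. The day 15/30 rule and its bearing on endpoint 8 are lesser points of reconciliation.

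**What to change.** - **Section 4.2.1:** state that RNA extraction and qPCR cover every scheduled swab (days 1, 2 if taken, 4, 7, 10, and 15/30 where collected), with sequencing wherever there is enough RNA. Replace the undefined last swab with day 10 and name it as the co-primary sample.
- **Sections 3.1 and 4.2.1 and Appendix 1:** reconcile the day 15/30 swab rule. If it stays conditional, name the test and the timing that trigger it, and say how endpoint 8 treats a patient first negative at day 10.
- **Endpoint 9:** refer to resistance to oseltamivir or baloxavir, and tabulate neuraminidase and PA variants separately by arm.

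The cost is protocol wording, plus qPCR on 60 intermediate patient-visits (90 if everyone attends day 2) and sequencing where RNA suffices, all on swabs already scheduled. Sections 2.1 and 3.1 already imply most of this work. Up to 60 further patient-visits are assayed if day 15/30 swabs are taken from everyone. No visits are added. Because the assays are batched at the end, the change is best made before laboratory work begins.
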